## 9.4.4. Safety Assessments

Safety assessments during the study will consist of AE and SAE monitoring, weight, clinical laboratory tests, vital signs, physical examinations, and 12-lead ECGs, as detailed in section 9.4.1.

## 9.4.4.1. Adverse Events

As defined by the ICH Guideline for GCP, an AE is any untoward medical occurrence in a patient or clinical investigation subject administered a pharmaceutical product, which does not necessarily have to have a causal relationship with treatment.

An AE can be:

- Any unfavorable and unintended sign (including an abnormal laboratory finding), symptom, or disease temporally associated with the use of a medicinal product, whether or not considered related to the medicinal product.
- Any new disease or exacerbation of an existing disease.
- Any deterioration in non-protocol-required measurements of laboratory value or other clinical test (e.g., ECG or X-ray) that results in symptoms, a change in treatment, or discontinuation from SM.
- Recurrence of an intermittent medical condition (e.g., headache) not present at baseline.

AEs fall into the categories of "non-serious" and "serious". Surgical procedures are not AEs; they are therapeutic measures for conditions that require surgery. The condition for which the surgery is required is an AE, if it occurs or is detected during the study period.

AEs or SAEs that are ongoing at the subject's last study visit must be followed until resolution or if, in the medical judgment of the Investigator, the event has stabilized or is assessed as chronic.

## 9.4.4.1.1. Reporting of Adverse Events

All subjects will be closely questioned regarding the occurrence of AEs.

For subjects who receive SM, all AEs (learned of through spontaneous reports or subject interview) will be collected starting from the first dose of SM until the end of the study. All AEs will be collected on the AE Case Report Form (CRF). All SAEs will be reported to the Sponsor.

A cluster of signs and symptoms that results from a single cause may be reported as a single AE (e.g., fever, elevated WBC, cough, abnormal chest X-ray, etc. can all be reported as "pneumonia").

### 9.4.4.1.2. Criteria for Assessing Severity

The Investigator will evaluate the comments of the subject and the response to treatment in order that he/she may judge the true nature and severity of the AE. Severity refers to the accumulated intensity of discomfort / impairment of health since the last recording of AEs and will be assessed according to the following criteria:

Mild: Awareness of sign, symptom, or event, but easily tolerated

**Moderate:** Discomfort enough to interfere with usual activity and may warrant intervention

**Severe:** Incapacitating with inability to do usual activities or significantly affects clinical status and warrants intervention

The criteria for assessing severity are different from those used for seriousness (see Section 9.4.4.2. for the definition of an SAE).

## 9.4.4.1.3. Criteria for Assessing Causality

The question of the relationship of an AE to SM should be determined by the Investigator or study physician after thorough consideration of all facts that are available. Assessment of causality is based on considering associative connections (time or place), pharmacological explanations, previous knowledge of the drug, presence of characteristic clinical or pathological phenomena, exclusion of other causes, and/or absence of alternative explanations. The causal relationship of an AE to SM will be assessed according to the following criteria (based on World Health Organization [WHO] definitions):

The Investigator is responsible for determining the relationship between the administration of SM and the occurrence of an AE as not suspected or suspected.

- **Not suspected:** The temporal relationship of the AE to SM administration makes a **causal relationship unlikely**, or other drugs, therapeutic interventions, or underlying conditions provides a sufficient explanation for the observed event.
- Not related: Temporal relationship to SM administration is missing or implausible, or there is an evident other cause.
- **Unlikely related**: Temporal relationship to SM administration makes a causal relationship improbable; and other drugs, chemicals, or underlying disease provide plausible explanations
- **Suspected:** The temporal relationship of the AE to SM administration makes a causal relationship possible, and other drugs, therapeutic interventions, or underlying conditions do not provide a sufficient explanation for the observed event.
- **Possibly related:** Reasonable time sequence to administration of SM, but event could also be explained by concurrent disease or other drugs or chemicals. Information on drug withdrawal may be lacking or unclear.
- **Definitely related:** Plausible time relationship to SM administration; event cannot be explained by concurrent disease or other drugs or chemicals. The response to withdrawal of the drug (dechallenge) should be clinically plausible. The event must be definitive pharmacologically or phenomenological, using a satisfactory rechallenge procedure if necessary.

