## 9.7.1.4.1. Adverse Events

AEs will be classified into standardized medical terminology from the verbatim description (Investigator term) using the Medical Dictionary for Regulatory Activities (MedDRA). AEs will be presented in the summary tables by preferred term nested within System Organ Class (SOC). Verbatim description and all MedDRA level terms, including the lower level terms, for all AEs will be contained in the subject data listings.

Data for AEs will be analyzed using the treatment-emergent signs and symptoms (TESS) philosophy. TESS are defined as AEs that:

- emerge during treatment, having been absent at pretreatment, or
- reemerge during treatment, having been present at pretreatment but stopped prior to treatment, or
- worsen in severity during treatment relative to the pretreatment state, when the AE is continuous.

Only treatment-emergent AEs (TEAEs) from the study will be summarized in tables. TEAEs will be summarized by presenting, for each treatment group, the incidence of AEs. The incidence of TEAEs will be based on the numbers and percentages of subjects with TEAEs. Although a MedDRA term may be reported more than once for a subject, that subject will be counted only once in the incidence count for that MedDRA term.

Separate TEAE incidence tables will be presented for the Baseline and Randomization Period, Dose Treatment Period, and combined Baseline and Randomization and Dose Treatment Periods. For the combined Baseline and Randomization and Dose Treatment Periods, the incidence of TEAEs will also be presented by highest severity reported, closest relationship to SM reported, and the dose of SM at first occurrence. For treatment-related TEAEs only, i.e., those TEAEs classified as possibly or definitely related to SM, the incidence rates will also be summarized as described previously for all TEAEs. Listings (and tabular summaries, if warranted) of deaths, other SAEs, and other significant AEs, including AEs resulting in treatment discontinuation, will be provided.

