### 6.1.1 Overall Study

Adverse events that occur or worsen after the first administration of study medication are considered treatment-emergent and will be summarized in tables. For missing information, the most conservative interpretation will be assumed. For example, if AE onset time is not collected, the AE starts on the first study dose date.

AEs will be summarized for each treatment group by presenting the incidence of AEs based on the number and percentage of subjects with AEs.

Table 14.3.1.1.1 will provide overall incidence of AEs for the Safety population. Table 14.3.1.1.2 will provide an incidence summary of AEs by System Organ Class, and Preferred Term for the Safety population.

Table 14.3.1.1.3 will provide an incidence summary of AEs by System Organ Class, Preferred Term, and Relationship to Study Drug for the Safety population. If a subject had two or more adverse events in the same system organ class (or with the same preferred term) with different relationships to study drug, then the event with the closest relationship to study drug will be used for that subject.

Table 14.3.1.1.4 will provide an incidence summary of AEs by System Organ Class, Preferred Term, and Severity for the Safety population. If a subject had two or more adverse events in the same system organ class (or with the same preferred term) with different levels of severity, then the event with the worst severity will be used for that subject.

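### The protocol's two causality scales overlap for adverse events that another cause sufficiently explains, and nothing says which scale governs the treatment-related count

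*Protocol*

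**What the plan says.** Protocol 9.4.4.1.3 makes the investigator responsible for "determining the relationship between the administration of SM and the occurrence of an AE as not suspected or suspected". It then defines six terms in one list: the two calls and four finer levels.

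- **Not suspected:** timing makes causation unlikely, "or other drugs, therapeutic interventions, or underlying conditions provides a sufficient explanation for the observed event". The two limbs are alternatives, so the second is enough whatever the timing.
- **Suspected:** timing makes causation possible and, as a second condition, "underlying conditions do not provide a sufficient explanation for the observed event" (the same is asked of other drugs and interventions).
- **Not related:** either the link in time is absent or not credible, or another cause is evident.
- **Unlikely related:** both limbs are needed, improbable timing and plausible alternatives.
- **Possibly related** is worded as follows: "Reasonable time sequence to administration of SM, but event could also be explained by concurrent disease or other drugs or chemicals".
- **Definitely related:** plausible timing, no other explanation, a plausible response to withdrawal, and a pharmacologically or phenomenologically definitive event, with rechallenge if needed.

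Protocol 9.7.1.4.1 defines treatment-related events as "those TEAEs classified as possibly or definitely related to SM" and summarises their incidence separately. SAP 6.1.1 tabulates events by relationship (Table 14.3.1.1.3). Where a subject has several events in a class or term, "then the event with the closest relationship to study drug will be used for that subject". SAP 6.1.2 repeats that table by sex, race and ethnicity. The SAP text neither redefines the levels, nor maps one scale to the other, nor restates which levels count as treatment-related.

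**The concern.** A causality scale should give each event one place. Here a rater who starts from the two-level call and a rater who goes straight to the finer levels can both follow the protocol and put the same event on opposite sides of the treatment-related line. About five sites will apply the definitions.

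Safety is the primary objective, and the relationship field feeds the treatment-related summaries and every relationship table. The protocol requires no record of which definition a rater applied, so analysts could not undo the inconsistency afterwards.

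**Working it through.** The plan states no treatment-related rate, so there is no figure to reproduce. The check takes the definitions in Protocol 9.4.4.1.3 as conditions and crosses three states of timing with four states of alternative explanation, giving 3 × 4 = 12 combinations.

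| Timing | Other explanation | Two-level call | Finer levels met |
|---|---|---|---|
| Missing or implausible | any of the four | Not suspected | Not related |
| Improbable | none | Not suspected | none |
| Improbable | plausible, not sufficient | Not suspected | Unlikely |
| Improbable | sufficient, not evident | Not suspected | Unlikely |
| Improbable | evident | Not suspected | Not related and Unlikely |
| Reasonable | none | Suspected | Definitely, if its further proof is met; otherwise none |
| Reasonable | plausible, not sufficient | Suspected | Possibly |
| Reasonable | sufficient, not evident | Not suspected | **Possibly** |
| Reasonable | evident | Not suspected | **Not related and Possibly** |

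The first row stands for four combinations.

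**Overlap.** Two of the 12 combinations meet both Not suspected and Possibly related. When the alternative is sufficient but not evident, Possibly related is the only finer level that fits: Unlikely related needs improbable timing, and Not related needs missing or implausible timing or an evident cause. When the alternative is evident, Not related and Possibly related both fit.

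**No overlap.** With reasonable timing and a plausible but insufficient alternative, the scales agree on Suspected and Possibly related.

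**Gap.** A well-timed event with no alternative explanation is Suspected. Without dechallenge or rechallenge evidence, for example because dosing continued, it cannot meet Definitely related. Possibly related presumes another explanation. Both finer levels it might be given count as treatment-related, so the related/not-related split does not move; only the level shown in Table 14.3.1.1.3 is uncertain. The improbable-timing row with no other explanation also lacks a finer level, but it stays on the Not suspected side.

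**Scale.** Group size is about 25 (Protocol 9.7.2). Subjects are counted once, so a subject changes the rate only if every related event they have, or every one under the class or term in question, is of the overlapping kind. With k such subjects the group's rate moves by k/25:

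- k = 1: 1/25 = 4.0 percentage points
- k = 2: 2/25 = 8.0
- k = 3: 3/25 = 12.0

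The documents give no value for k.

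**The case against.** The strongest reply is that an event another cause could explain is not an event it sufficiently explains. If Possibly related is read as a subdivision of Suspected, it excludes sufficient alternatives and the clash disappears. That is a sensible reading, and it defeats the broader claim a reader might infer, that every well-timed event with some plausible alternative is classed both ways. It does not remove the narrower problem. No sentence nests the finer levels under the two calls or sets the order of assessment; the nesting is inferred from list order and from 9.7.1.4.1 pairing Possibly with Definitely. Taken alone, the wording of Possibly related has no upper limit on how good the other explanation may be.

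A second reply is that an event sufficiently explained by something else belongs in Not related, because the protocol never separates sufficient from evident. If the two are treated as the same, the first overlapping case merges into the second, where Not related and Possibly related still both fit.

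A third is that the eCRF specifications and completion instructions are not among the documents and may settle the matter. This stands as a limit: a form that opens the finer levels only after the two-level call would largely prevent the divergence. A form with only the four levels would leave the evident-cause overlap. A form with only the two-level call would leave the rule in 9.7.1.4.1 with no field to use.

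The consequence is also bounded. Safety p-values are descriptive (SAP 6), sites are pooled (SAP 4), and investigators are blinded (Protocol 9.5.4), so inconsistent labelling need not favour either arm.

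**Conclusion.** The defect is real but narrow. The scales conflict only for well-timed events with a sufficient or evident other cause. Each subject whose only related event is of that kind moves a group's treatment-related rate by 4 percentage points at about 25 per group. The documents do not say how many there would be, and any overall range would need guessed shares of well-timed and otherwise explained events. The unexplained-event gap affects the by-level relationship table only.

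A reader might infer that the treatment-related rate is uninterpretable. The documents do not support that: the overall, class-and-term and severity incidence tables do not use causality, and the relationship tables would still place the non-overlapping events consistently. What is at stake is avoidable misclassification in a descriptive summary that serves the primary objective.

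The conclusion assumes that raters use the protocol wording as it stands and that no unseen form or instruction sets precedence. It is worth correcting because later analysis cannot repair it and the correction is cheap.

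**What to change.** Record the four-level item and derive the two-level call from it: Not suspected = Not related + Unlikely related; Suspected = Possibly related + Definitely related. Then in Protocol 9.4.4.1.3:

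- Keep the sufficient-explanation limbs of Not suspected and Suspected. Deleting them might seem simpler, but it would leave the overlap between Not related and Possibly related untouched.
- Limit Possibly related to reasonable timing where any alternative is neither sufficient nor evident, and extend it to events with no alternative explanation that do not meet Definitely related.
- Widen Not related or Unlikely related to take every event with a sufficient or evident other cause, whatever its timing. State which of the two prevails when both fit, and let Unlikely related take improbable timing with no other explanation, so that every event has exactly one level.

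Carry the mapping, and the rule that treatment-related means Possibly or Definitely, into SAP 6.1.1. Align the CRF completion instructions.

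The cost is a wording change in the protocol and CRF instructions and a sentence or two in the SAP. The treatment-related rate may shift slightly. Sample size and significance level are unaffected. The wording must change before events are rated.

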### 9.4.4.2. Serious Adverse Events

A SAE is any untoward medical occurrence that at any dose:

- results in death;
- is life-threatening (i.e., the subject was at immediate risk of death from the AE as it occurred. This does not include an event that, had it occurred in a more severe form or was allowed to continue, might have caused death.);

- requires inpatient hospitalization or prolongation of existing hospitalization;
- results in persistent or significant disability/incapacity; or
- is a congenital anomaly/birth defect (in the child of a subject who was exposed to the SM)
- is a medically important event or reaction (see below)

Other important medical events that may not be immediately life-threatening or result in death or hospitalization, but when based on appropriate medical judgment, may jeopardize the subject or may require intervention to prevent one of the outcomes in the definition of SAE listed above should also be considered SAEs. Examples of such events are intensive treatments in an emergency room or at home for allergic bronchospasm, blood dyscrasias, or seizures that do not result in hospitalization, or development of drug dependency or drug abuse. These events may be considered to need rapid reporting by the Sponsor to regulatory authorities (see Section 9.4.4.2.2.).

Any new SAEs reported by the subject that occur after the first dose of SM and until the end of the study will be collected. SAEs that are ongoing at the subject's last study visit must be followed until resolution or if, in the medical judgment of the Investigator, the event has stabilized or is assessed as chronic.

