## 8. STUDY OBJECTIVES

### **Primary Objective**

The primary objective is to determine the safety of SPN-812V in adults with ADHD.

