## 9.3.1 Inclusion Criteria

Subjects meeting all of the following criteria may be included in the study:

- 1. Able to provide informed consent prior to any study procedure being conducted.
- 2. Capable and willing to comply with study procedures.
- 3. Male or female aged 18 to 64, inclusive.
- 4. Subjects with a current diagnosis of ADHD as confirmed by the Conners' Adult ADHD Diagnostic Interview for DSM-IV (CAADID)
- 5. Clinical Global Impression Severity (CGI-S) score of 4 or higher.
- 6. On no treatment for ADHD or willing to be withdrawn from an ongoing treatment after a washout of at least 10 days.
- 7. Body Mass Index (BMI) between 18.0 and 34.0 inclusive
- 8. Subject must be in general good health as determined by medical history, ECG, and other analysis that, in the judgment of the Investigator, would confirm the Subject's good health.
- 9. Females of childbearing potential (FOCP) who, if sexually active, agree to use acceptable forms of contraception (including oral, transdermal, or implanted contraceptives; intrauterine device; female condom with spermicide; diaphragm with spermicide; cervical cap; abstinence; use of condom with spermicide by sexual partner or sterile [at least 6 months prior to SM administration] sexual partner) at least 14 days prior to start of study drug administration, throughout the study, and for 30 days following the last dose of SM.
- 10. Postmenopausal females with amenorrhea for at least 2 years or females who are permanently sterilized (e.g., tubal occlusion, hysterectomy, bilateral salpingectomy).

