### 9.4. Study Methods

### 9.4.1. Schedule of Visits and Procedures

Table 1. Schedule of Visits and Procedures presents the schedule of visits and procedures for the study.

Study Phase	Screening	Dose Treatment Period		End of Study b
	Period	(Visit window +/- 2 days)		
Activity	Visit 1 Up to 14 Days Prior to Visit 2	Visit 2	Visits 3 – 8	
Informed Consent a	Х			
Medical and Psychiatric History and Demographics	х			
Physical Exam	Х			Х
ECG (12-lead)	Х		Хc	Х
Vital Signs d	Х	Х	Х	Х
Hematology	Х			Х
Urinalysis and drug screen	Х			Х
CYP2D6 Enzyme Activity Screening	Х			
Serum Chemistry	Х			Х
Serum Pregnancy Test (for FOCP only)	х			Х
Urine Pregnancy Test (for FOCP only)		х		
CAADID	Х			
CGI	Х	Х	Х	Х
C-SSRS	Х	Х	Х	Х
CAARS e		Х	Х	Х
Concomitant Medication	Х	Х	Х	Х
Randomization		Х		
SM Dispensed		Х	Х	
SM Diary Dispensed			Xf	
Optional SM Administered On-Site g			х	
Optional PK Blood Sampling			X h	
Adverse Events			Х	Xi

a To be obtained prior to any study procedures being performed.

b To be performed at the end of Visit 8 (unless done previously during Visit 8), or at early discontinuation.

C At Visit 4 only

d Heart rate, seated blood pressure, temperature, and respiratory rate will be measured at every visit. The vital signs readings will be performed within approximately 10 minutes prior to the scheduled blood draws, where applicable. Height will be taken at screening and weight will be assessed at each visit.

e CAARS self-report done only at Visits 2 and 8, CAARS investigator-report done at Visits 2-8

 $f \qquad \mbox{At Visit 7 to record SM taken prior to Visit 8. \ \mbox{Diary to be collected at Visit 8}.$ 

- g Dose to be administered on-site after the pre-dose draw and an overnight fast at Visit 8; subjects may eat 2 hours after dosing.
- h At Visit 8, subjects who wish to participate will be dosed after an overnight fast and have a series of PK samples drawn. Samples will be taken pre-dose, and at Hours ½, 1, 2, 3, 4, 5, and 6.
- i Any subject who experiences an adverse event (whether serious or non-serious) or has a clinically significant abnormal laboratory test value(s) will be followed by the Investigator at appropriate intervals based on the severity and nature of the event, until resolved, or when the condition is assessed as stable, causality other than the SM has been found, or the subject is referred to another health care professional.

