## 9.4.4.2.2. Other Events Requiring Immediate Reporting

The Investigator must report a pregnancy that occurs in a subject during a clinical study to the Medical Monitor within 24 hours of first becoming aware of the event. The Investigator should discuss the case with the Medical Monitor; the Investigator must follow any pregnant subject for 3 months after the child is born. Any AEs concerning the pregnancy of the subject during pregnancy or the child after birth must be documented and reported to the Sponsor.

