### 6.6 PRIOR AND CONCOMITANT MEDICATIONS

A table (Table 14.3.7) summarizing frequencies of prior and current use of concomitant medications will be presented for the safety population and its treatment group subsets.

Prior and Concomitant medications and therapies that are ongoing as of the date of informed consent and all medications taken since the time of dosing of SM until the end of the study (the last visit) will be listed (Listing 16.2.12). If non-SM's taken time is not collected, the medication taken on and after the first dose date of SM until the end of study will be listed. Concomitant medications will be assigned an 11-digit code using the WHO Drug Dictionary (WHO DD) drug codes. Concomitant medications will be further coded to the appropriate Anatomical-Therapeutic-Chemical (ATC) code indicating therapeutic classification.

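### New adverse events are collected only to Visit 8, hours after the last dose, and for PK participants possibly with no adverse-event assessment after the on-site active dose

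*Protocol*

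**What the plan says.** Safety is the primary purpose of the trial: "The primary objective is to determine the safety of SPN-812V in adults with ADHD" (Protocol section 8).

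**Collection window.** Under Protocol 9.4.4.1.1, AEs "will be collected starting from the first dose of SM until the end of the study". Protocol 9.4.4.2 sets the same window for new SAEs: "Any new SAEs reported by the subject that occur after the first dose of SM and until the end of the study will be collected". Events already ongoing at the last visit are followed until they resolve or are judged stable or chronic.

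**Where the study ends.** The synopsis calls Visit 8 the final visit, and no later visit or call appears in either document. Note b to Table 1 says of the end-of-study assessments: "To be performed at the end of Visit 8 (unless done previously during Visit 8), or at early discontinuation". SAP 6.6, in its rule for listing medications, runs "until the end of the study (the last visit".

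**Dosing up to that point.** Subjects outside the PK sub study take their last dose the evening before Visit 8 (Protocol 9.1.2, 9.5.1). Every PK participant, whichever arm they were randomised to, takes active drug on site on the morning of Visit 8 (9.5.1, 9.5.5). Protocol 9.4.3 describes this as a first dose for the placebo group.

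**Order of assessments.** Protocol 9.4.1.3.2 lists the AE assessment among the general Visit 8 evaluations, ahead of the PK procedures. Section 9.4.1.4 says assessments completed at Visit 8 are not repeated.

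**Pregnancy.** "The Investigator must report a pregnancy that occurs in a subject during a clinical study" (9.4.4.2.2). A serum test is done at end of study. Contraception is required throughout the study "and for 30 days following the last dose of SM" (9.3.1).

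**The concern.** In a trial whose primary objective is safety, active dosing continues up to the last contact, or takes place during it, and nothing is planned afterwards to find a new event. There are three gaps.

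1. Events that begin after the drug is stopped, including delayed and discontinuation events, have no planned route into the database.
2. A placebo subject in the PK sub study takes active drug for the first and only time at Visit 8. If the AE assessment has already been done, nothing in the schedule requires another that day.
3. A pregnancy that begins after Visit 8 but within the 30-day contraception period is outside the reporting rule. One that began earlier but is too recent to test positive at the final visit falls within the rule, but no planned contact would reveal it.

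There is also an attribution gap. SAP 4.2 and section 6 summarise safety by treatment actually received, and SAP 6.1.1 counts an event as treatment-emergent if it follows the first study medication. Neither says which column holds an event in a placebo subject after the active PK dose.

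**Working it through.** The plan states no figure for post-dose observation, so there is none to reproduce. The check is one of text and timing.

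**Inputs from the documents**
- Elimination half-life about 3 h and Tmax about 100 min (Protocol 9.4.3, from a single 100 mg dose in ten healthy volunteers).
- Last PK sample 6 h after the dose; blood drawn over approximately seven hours (synopsis).
- Last dose outside the sub study: the evening before Visit 8.
- 50 randomised, 20% dropout, 40 completers expected (Protocol section 7).

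**Assumptions**
- 10 to 14 h from evening dose to Visit 8, because clock times are not given.
- PK participants observed until 6 to 7 h after the dose. The documents fix the last sample at 6 h but give no departure time.

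**Fraction of drug remaining by simple decay, 0.5^(t/3)**

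| Time since dose | Half-lives | Remaining |
|---|---|---|
| 6 h | 2.0 | 25% |
| 7 h | 2.3 | 20% |
| 10 h | 3.3 | 10% |
| 14 h | 4.7 | 4% |
| 15 h | 5.0 | 3% |

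**Level relative to peak after the PK dose.** Assume a one-compartment oral model with ke = ln 2/3 = 0.231 per h. A ka of 1.24 per h gives Tmax = ln(1.24/0.231)/(1.24 − 0.231) = 1.67 h, or 100 min. Concentration is proportional to exp(−ke·t) − exp(−ka·t):
- at 1.67 h: 0.680 − 0.127 = 0.554
- at 6 h: 0.250 − 0.001 = 0.249, so 0.249/0.554 = 45% of peak
- at 7 h: 0.198 − 0.000 = 0.198, so 0.198/0.554 = 36% of peak

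These figures describe residual drug. They do not count missed events.

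**Chance that something occurs unseen.** The documents give neither the number of placebo PK participants nor an event rate. For scale, let n placebo subjects take the PK dose, and let each have probability p of a new event after observation ends. The chance of at least one such event is 1 − (1 − p)^n. With equal dropout, 40/2 = 20 placebo completers is the expected ceiling for n.

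| n | p = 1% | p = 5% | p = 10% |
|---|---|---|---|
| 5 | 5% | 23% | 41% |
| 10 | 10% | 40% | 65% |
| 20 | 18% | 64% | 88% |

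**Observed time after the dose.** The contraception period is 30 × 24 = 720 h. Against it, 6 to 7 h is 0.8% to 1.0%, and 10 to 14 h is 1.4% to 1.9%. The comparison gives scale only, because the protocol does not set 30 days as an AE window.

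**Text check.** Only the efficacy assessments are required to precede PK dosing; the timing of the AE assessment within Visit 8 is left open. With the no-repeat rule in 9.4.1.4, a site that asks about AEs first thing and then doses has met the schedule.

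**The case against.** A reader might infer that the primary safety objective cannot be met. The documents do not support that. The primary endpoint is safety after 6 weeks of treatment, and the listed analyses compare 6-week data with placebo. Those data are collected. The PK dose comes after that comparison, is optional and has its own consent.

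A reader might also infer that pregnancy capture stops at Visit 8. It does not. Section 9.4.4.2.2 runs from the site's awareness with no cut-off, covers any pregnancy that begins during the study, requires follow-up to 3 months after birth, and is backed by a serum test at end of study. Only pregnancies that start after Visit 8, or are too early to detect there and never volunteered later, escape.

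Further objections stand in part:
- The end of the study is not defined for AE collection. Visit 8 is inferred from the schedule, and the SAP gloss sits in a medication rule. A looser reading does not help, since no later contact would bring new events to light.
- SAE reporting within 24 hours of awareness (9.4.4.2.1) has no end date, so an event that a subject volunteers could still reach the sponsor. Nothing prompts the subject to volunteer it.
- For early discontinuers the interval from last dose to final assessment is not given, so a gap of only hours is shown only for those who reach Visit 8.
- PK sampling covers Tmax and two half-lives, so acute effects near peak should be visible to site staff. Outside the sub study, most of the drug has cleared by Visit 8 under the assumed timing.
- The 30-day figure concerns contraception. No section applies it to AEs.

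**Conclusion.** The point holds for new-onset events. No contact is planned after Visit 8. Subjects who reach it are then about 10 to 14 h (assumed) past the last evening dose, or about 6 to 7 h past the on-site active dose. At 6 to 7 h, on the protocol's half-life and Tmax and a one-compartment model, the level is still about 45% to 36% of peak. For placebo PK participants that dose is the only active exposure, and no AE assessment need follow it.

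The randomised 6-week safety comparison stands. Pregnancies that begin during the study are already reportable. The number of events that would be missed cannot be derived from the documents, because the sub study is optional and no event rate is given.

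This is an inexpensive improvement the sponsor should make. It rests on reading the end of the study as Visit 8. If something else was meant, the wording needs defining anyway.

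**What to change.** 1. In Protocol 9.4.4.1.1 and 9.4.4.2 and SAP 3.6.1, define the end of AE and SAE collection as a stated interval after the last dose of study medication, counting the PK dose.
2. In Protocol 9.4.1.3.2, require an AE assessment after the last PK draw.
3. Add one telephone contact per subject, by existing site staff, at the end of that interval, asking about new AEs, SAEs and pregnancy. Thirty days would match the contraception period, but that is a choice for the sponsor. A long interval leans more on recall for the evening after the PK dose, which the assessment in item 2 only partly offsets.
4. In the SAP, list post-treatment events and post-PK-dose events separately by randomised arm, so that an event in a placebo subject after the active PK dose is not counted as a placebo event.

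While SAP 3.6.1 is open, reconcile it with Protocol 9.4.4.1.1. The SAP starts AE collection at consent and reports only SAEs at least possibly related to study medication. The protocol starts at first dose and reports all SAEs.

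Cost: about 50 calls, a protocol amendment with IRB approval, and database lock later by up to the chosen interval for the last subject. No visit, sample or dose changes.
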